7.1.1 Adverse Events of Special Interest and Other Potential Risks

There is one identified important potential risk of Progressive Multifocal Leukoencephalopathy. There are 6 other identified potential risks: immunotoxicity, immunogenicity, infection, vascular and thrombotic events, local tolerability, and malignant tumors. Potential risks will be summarized by treatment group as listed in Appendix 16.6. Important potential risks will be listed.

7.1.1.1 Hypersensitivity

Potential hypersensitivity reactions such as serum sickness, vasculitis, or Arthus reactions to ontamalimab will be regarded as adverse events of special interest (AESI). An external hypersensitivity adjudication committee is established to review reported hypersensitivity events and adjudicate whether the event was a hypersensitivity event, which type (Type I or Type III) of event it was, and recommendations of permanent discontinuation or re-challenge with IP. Reported hypersensitivity events, adjudicated hypersensitivity events, and study drug recommendation will be summarized by treatment groups as listed in Appendix 16.6.

The number of hypersensitivity reactions and percentage of subjects with hypersensitivity reactions as adjudicated will be summarized by treatment group and ontamalimab all doses; and by SOC, preferred term, and hypersensitivity type. Reported hypersensitivity events and adjudicated hypersensitivity events will be listed for the Safety Set.

7.2 Clinical Laboratory Data

Descriptive statistics for clinical laboratory values (in conventional units) and changes from induction study (SHP647-301 or SHP647-302) baseline at each assessment time point for quantitative variables will be presented by treatment group as listed in Appendix 16.6 for the following clinical laboratory variables. The number and percentage of subjects for qualitative variables in urinalysis will be presented by treatment group as listed in Appendix 16.6 in the Safety Set.

Serum chemistry

- alkaline phosphatase
- aspartate aminotransferase (AST)
- alanine aminotransferase (ALT)
- total bilirubin
- total protein
- albumin
- glucose
- blood urea nitrogen
- creatinine
- sodium
- potassium
- chloride
- calcium
- carbon dioxide

Hematology

- hemoglobin
- hematocrit
- mean corpuscular hemoglobin
- mean corpuscular hemoglobin concentration
- mean corpuscular volume
- erythrocyte (red blood cell) count
- leukocyte (white blood cell) count
- neutrophils
- lymphocytes
- monocytes
- eosinophils
- basophils
- platelet count

Urinalysis

- glucose
- protein
- specific gravity
- pH
- nitrite
- bilirubin
- ketones
- hemoglobin
- urobilinogen
- leukocyte esterase

Clinical laboratory test values are potentially clinically important (PCI) if they meet either the low or high PCI criteria listed in Table 3. The number and percentage of subjects with post-MNT baseline (value collected after the first exposure to IP in the SHP647-303 study) PCI values will be tabulated by treatment group as listed in Appendix 16.6. The percentages will be calculated relative to the number of subjects with at least 1 post-MNT baseline assessment. The numerator is the total number of subjects with at least 1 post-MNT baseline PCI value. A supportive listing of subjects with post-MNT baseline PCI values will be provided including the subject number, site, induction study (SHP647-301 or SHP647-302) baseline, MNT baseline, and post-MNT baseline values.

Figures will be presented for hematology and chemistry to show the changes in laboratory parameters over time. Data will be presented as box-and-whisker plots by treatment group as listed in Appendix 16.6 at each visit, with 1 laboratory parameter per page.

Shifts from induction study (SHP647-301 or SHP647-302) baseline category to each visit will be presented by treatment group as listed in Appendix 16.6 for hematology, chemistry, and urinalysis. For hematology and chemistry, shifts will be categorized as Low, Normal, or High. For urinalysis, shifts will be categorized as Abnormal or Normal.

All laboratory data will be listed for the Safety Set.

Table 3: Criteria for Potentially Clinically Important Laboratory Tests

Parameter	Age Range	Sex	Outlier Criteria ^a	
			Low	High
Hematology				
Hemoglobin	All		<8 g/dL	NA
Hematocrit	All		<32%	NA
MCH	All		<LLN	>ULN
MCHC	All		<LLN	>ULN
MCV	All		<LLN	>ULN

Table 3: Criteria for Potentially Clinically Important Laboratory Tests

Parameter	Age Range	Sex	Outlier Criteria ^a	
			Low	High
Erythrocyte (RBC)	All		<3.0 x 10 ⁶ /μL	NA
Leukocytes (WBC)	All		<3.0 x 10 ³ /μL	>20 x 10 ³ /μL
Neutrophils (Abs)	All		<1.5 x 10 ³ /μL	>15 x 10 ³ /μL
Neutrophils (%)	All		<40%	NA
Lymphocytes (Abs)	All		NA	NA
Lymphocytes (%)	All		<10%	>50%
Monocytes (Abs)	All		NA	NA
Monocytes (%)	All		NA	>25%
Eosinophils (Abs)	All		NA	NA
Eosinophils (%)	All		NA	>10%
Basophils (Abs)	All		NA	NA
Basophils (%)	All		NA	>10%
Platelets	All		<75 x 10 ³ /μL	>1,000 x 10 ³ /μL
Chemistry				
Alkaline Phosphatase	All		NA	>2.5 x ULN (or alternatively >400 U/L)
Aspartate Aminotransferase (AST)	All		NA	>2.5 x ULN
Alanine Aminotransferase (ALT)	All		NA	>2.5 x ULN
Total Bilirubin	All		NA	>1.5 x ULN
Total Protein, plasma or serum	All		<5 g/dL	>9 g/dL
Albumin	All		<3 g/dL	NA
Glucose (fasting)	All		<55 mg/dL	>160 mg/dL
Blood Urea Nitrogen (BUN)	All		NA	>2.5 x ULN (or alternatively >29.4 mg/dL)
Creatinine, serum	All		NA	>1.5 x ULN (or alternatively >1.98 mg/dL)
Sodium	All		<130 mEq/L	>150 mEq/L
Potassium, plasma or serum	All		<3 mEq/L	>5.5 mEq/L
Chloride	All		<90 mEq/L	>115 mEq/L
Calcium	All		<8.0 mg/dL	>11.2 mg/dL
Carbon dioxide (NCI uses bicarb)	All		NA	NA
DILI Screen (ongoing safety monitoring)	All		NA	AST or ALT >3 x ULN and TBL >2 x ULN
Urinalysis				
Bilirubin	All		NA	NA
Leukocyte esterase	All		NA	NA
Protein	All		NA	≥2+
Glucose	All		NA	NA

Table 3: Criteria for Potentially Clinically Important Laboratory Tests

Parameter	Age Range	Sex	Outlier Criteria ^a	
			Low	High
Blood	All		NA	NA
Ketones	All		NA	NA
Nitrite	All		NA	NA
pH	All		NA	NA
Specific gravity	All		NA	NA
Urobilinogen	All		NA	NA

LLN=lower limit of normal provided by the laboratory; NA=not applicable; ULN=upper limit of normal provided by the laboratory.

^a If criteria in both directions are shown for a single parameter, then abnormalities in each direction are summarized separately.

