5.2 Demographic and Other Baseline Characteristics

Descriptive summaries of demographic and baseline characteristics will be presented by treatment group as listed in Appendix 16.6 for the Safety Set, Ontamalimab Responder FAS, and Placebo Responder FAS.

Subject's age is from the induction study (SHP647-301 or SHP647-302), which is calculated as the difference between the date of birth and the date of informed consent in the induction study. If day of birth is missing then the day will be imputed as 1, if both the day and month of birth are missing then the day will be imputed as 1 and the month will be imputed as 1 (January). The following demographic characteristics will be summarized in the following order in the tables: age, age category (<18, 18 to <65 and ≥ 65 ; <35 and ≥ 35), sex (Male, Female), ethnicity (Hispanic or Latino, Not Hispanic or Latino, Not Reported, Unknown), region (North America, Western Europe, Eastern Europe, Asia (Japan/South Korea), ROW (Africa/Australia/Latin America/Middle East), race (American Indian or Alaska Native, Asian (Japanese, Korean, Other), Black or African American, White, Native Hawaiian or Other Pacific Islander, and Other), Japanese ancestry (Currently living in Japan, Born in Japan and currently living outside of Japan for less than 5 years, and Other), and Korean ancestry (Currently living in Korea, Born in Korea and currently living outside of Korea for less than 5 years, and Other).

Baseline is defined as the last assessment prior to the first administration of the IP in the induction study (SHP647-301 or SHP647-302) unless otherwise specified. Maintenance (MNT; SHP647-303) baseline is defined as the value for the assessment collected at the Week 12 visit of the induction study. The following baseline characteristics will be summarized:

- Weight,
- Height,
- Body mass index (BMI),
- UC disease duration and UC disease duration category (<1 year, ≥ 1 to <3 years, ≥ 3 to <7 years and ≥ 7 years)

Disease duration is calculated as the number of years from the date of UC diagnosis to the date of informed consent in the induction study (SHP647-301 or SHP647-302),

- UC disease location (Proctitis, Procto-Sigmoiditis, Left-sided Colitis, Extensive Colitis/Pancolitis),
- Total Mayo severity and total Mayo severity category (<6, 6 to <9, and ≥9),
- Total Mayo severity and total Mayo severity category at MNT baseline (<6, 6 to <9 and ≥9),
- Stool frequency score (0, 1, 2, and 3),

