7.5 Electrocardiogram (ECG)

Table 4: Criteria for Potentially Clinically Important Vital Signs

Vital Sign Parameter	Flag	Criteria ^a	
		Observed Value	Change from MNT Baseline
Systolic blood pressure (mmHg)	High	≥180	Increase of ≥20
	Low	≤90	Decrease of ≥20
Diastolic blood pressure (mmHg)	High	≥105	Increase of ≥15
	Low	≤50	Decrease of ≥15
Pulse rate (beats per minute)	High	≥120	Increase of ≥15
	Low	≤50	Decrease of ≥15
Weight (kg)	High	-	Increase of ≥7%
	Low	-	Decrease of ≥7%
BMI (kg/m ²)	High	-	Increase of ≥10%
	Low	<18	Decrease of ≥10%
Temp. (°C)		NA	NA

^a For pulse rate, a post-baseline value is considered as a PCI value if it meets both criteria for observed value and change from MNT baseline. For systolic/diastolic blood pressure, a post-baseline value is considered as a PCI value if it meets criteria for observed value or change from MNT baseline. For weight and BMI, a post-baseline value is considered as a PCI value if it meets criteria for change from MNT baseline.

A central ECG reader will be used. Descriptive statistics for ECG variables (eg, heart rate, PR interval, QRS interval, QT interval, QTc interval, QTcB, and QTcF) and their changes from induction study (SHP647-301 or SHP647-302) baseline at each assessment time point will be presented by treatment group as listed in Appendix 16.6.

Electrocardiogram interpretation will be summarized by visit. A shift table from induction study (SHP647-301 or SHP647-302) baseline to each visit for qualitative ECG results will be presented by treatment group as listed in Appendix 16.6.

Electrocardiogram variable values will be considered PCI if they meet or exceed the upper limit values listed in Table 5. The number and percentage of subjects with available induction study (SHP647-301 or SHP647-302) baseline values and post-MNT baseline PCI values will be tabulated by treatment group as listed in Appendix 16.6. The percentages will be calculated relative to the number of subjects with available induction study (SHP647-301 or SHP647-302) baseline values and at least 1 post-MNT baseline assessment. The numerator is the total number of subjects with at least 1 post-MNT baseline PCI value.

Listings of ECG data including the central reader's assessment and investigator's interpretation by individual subject will be produced. Separate listings will be produced for subjects with ECG results meeting the PCI criteria. Data from unscheduled visits will be listed, but not summarized.

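### The laboratory and ECG tables of potentially clinically important values mix new-onset with pre-existing abnormalities; add two rows by arm, and drop the induction-ECG condition in SAP 7.5

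*SAP*

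**What the plan says.** **Laboratory data (SAP 7.2).** "Clinical laboratory test values are potentially clinically important (PCI) if they meet either the low or high PCI criteria listed in Table 3". Table 3 sets limits on the observed value, either fixed or relative to the laboratory's normal limits, with no change-from-baseline condition. For the denominator, "The percentages will be calculated relative to the number of subjects with at least 1 post-MNT baseline assessment". For the numerator, "The numerator is the total number of subjects with at least 1 post-MNT baseline PCI value". SAP 12.5 adds that every assessment after MNT baseline feeds the PCI determination, so a long-standing abnormality needs to appear only once to count.

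**ECG (SAP 7.5).** "Electrocardiogram variable values will be considered PCI if they meet or exceed the upper limit values listed in Table 5". Table 5 has three limits: QRS at 150, PR at 250 and QTc at 500 msec. The numerator sentence is the same as for laboratory data. The denominator is narrower: "The percentages will be calculated relative to the number of subjects with available induction study (SHP647-301 or SHP647-302) baseline values and at least 1" assessment after MNT baseline. The induction value must exist but need not be within limits.

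**Baseline (SAP 5.2).** "Maintenance (MNT; SHP647-303) baseline is defined as the value for the assessment collected at the Week 12 visit of the induction study".

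**Related outputs.** The supportive laboratory PCI listing prints the induction "baseline, MNT baseline, and post-MNT baseline values". For laboratory categories, "Shifts from induction study (SHP647-301 or SHP647-302) baseline category to each visit will be presented by treatment group". ECG has a qualitative shift table, also from induction baseline, and a separate PCI listing whose baseline columns are not specified.

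**The concern.** These are the planned by-arm summaries of laboratory and ECG outliers during the maintenance study. A reader comparing arms wants to know who went beyond a limit after re-randomisation. The count as defined cannot show that, because it adds those subjects to those who were beyond the limit at MNT baseline and simply stayed there.

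Other parts of the plan do make the distinction. SAP 7.1 counts only adverse events that start at or after the first SHP647-303 dose. SAP 7.4 requires a change from baseline for pulse, weight and BMI. Protocol 8.1.6 singles out end-of-treatment abnormalities that were absent at the last pretreatment value.

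What is at stake is visibility. Protocol 9.5 states that no formal hypothesis testing of safety is planned, so no test is distorted. But with 366 subjects enrolled of 696 planned, the tables carry less information than intended, and a mixed count uses it less well.

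The ECG denominator is a second, smaller matter. It requires an induction baseline ECG although Table 5 has no change criterion for that value to serve.

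**Working it through.** The documents give no PCI rate for these tables, so there is no planned figure to reproduce. The check is the counting rule itself, followed by an illustration on assumed rates.

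**1. Counting rule.** Let p0 be the share of subjects already beyond a limit at MNT baseline, s the share of those who are beyond it again afterwards, and r the new-onset risk among the rest. Under SAP 7.2 the displayed proportion is

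displayed = p0 × s + (1 − p0) × r.

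**2. Dilution when pre-existing cases persist in both arms (s = 1).** Assumed new-onset risks are 10% and 5%: true ratio 2.0, true difference 5 points.

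| p0 | Higher-risk arm | Lower-risk arm | Displayed ratio | Displayed difference |
|---|---|---|---|---|
| 1% | 0.01 + 0.99 × 0.10 = 0.1090 | 0.01 + 0.99 × 0.05 = 0.0595 | 1.83 | 4.95 points |
| 5% | 0.05 + 0.95 × 0.10 = 0.1450 | 0.05 + 0.95 × 0.05 = 0.0975 | 1.49 | 4.75 points |
| 10% | 0.10 + 0.90 × 0.10 = 0.1900 | 0.10 + 0.90 × 0.05 = 0.1450 | 1.31 | 4.50 points |
| 20% | 0.20 + 0.80 × 0.10 = 0.2800 | 0.20 + 0.80 × 0.05 = 0.2400 | 1.17 | 4.00 points |

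The difference shrinks by the factor (1 − p0), much less than the ratio. Restricting numerator and denominator to subjects not beyond the limit at MNT baseline returns 2.0 at every p0.

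**3. Sensitivity to the assumptions.**
- Rarer new events are diluted more. At 4% vs 2% and p0 = 10%: (0.10 + 0.90 × 0.04) / (0.10 + 0.90 × 0.02) = 0.136 / 0.118 = 1.15.
- Partial persistence dilutes less. At 10% vs 5%, p0 = 10% and s = 0.5: (0.05 + 0.09) / (0.05 + 0.045) = 0.140 / 0.095 = 1.47, against 1.31 when all cases persist.
- At p0 = 0 nothing changes.

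**4. When persistence differs by arm.** For ontamalimab responders, MNT baseline is Week 12 on ontamalimab. Assume p0 = 20%, persistence of 100% on continued ontamalimab and 50% on placebo, and new-onset risk of 5% in both arms.
- All-subject count: 0.20 + 0.80 × 0.05 = 24% on ontamalimab; 0.20 × 0.50 + 0.80 × 0.05 = 14% on placebo.
- New-onset count alone: 5% vs 5%.

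Here the present count shows a contrast that a new-onset count would lose. Neither is sufficient alone.

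**5. ECG denominator.** A subject with no induction baseline ECG and a post-MNT QTc of 500 msec or more meets Table 5 but not the SAP 7.5 condition, and so is left out of both count and percentage. SAP 7.2 sets no such condition for laboratory data.

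**The case against.** **Much of the information is available elsewhere.** The laboratory PCI listing prints MNT baseline, so a reader can separate new from old cases by hand. For MCH, MCHC and MCV the Table 3 limits are the normal-range limits, so, if the shift tables use the same ranges, their normal-to-low and normal-to-high cells come close to a new-onset count. Laboratory or ECG changes judged clinically significant also become adverse events under Protocol 8.1.6. This stands, and it rules out saying that new abnormalities are hidden. It does not close the gap: a listing gives no rate by arm, and the shift tables work visit by visit from induction baseline, before re-randomisation. Apart from a few parameters, they do not use PCI limits.

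**The size is assumed.** Neither p0 nor any event rate is in the documents. Several limits are extreme, exclusion criterion 9 removes some subjects with laboratory or ECG abnormalities, and the SAP plans counts and percentages rather than ratios. All of this stands.

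**Equal pre-existing prevalence is not guaranteed.** The pooled SHP647-303 groups in SAP Appendix 16.6 combine different induction histories. By the planned numbers, 296 / (296 + 104/5) = 93% of placebo subjects had induction ontamalimab, against 148 / (148 + 104 × 2/5) = 78% of each active group. Dilution is therefore the expected effect only under similar prevalence and persistence.

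**A new-onset rate should not displace the present count.** A reader might infer that it should become the main PCI result. The design does not support that. Step 4 of the working shows an abnormality that persists on drug and resolves on placebo disappearing from a new-onset count. A subject already abnormal who worsens would also drop out.

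**Conclusion.** The point holds as a cheap improvement to the safety summary. The laboratory and ECG PCI tables combine new-onset and pre-existing abnormalities, and no planned table gives a new-onset PCI rate by arm relative to MNT baseline.

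If pre-existing cases persist similarly in both arms, a true ratio of 2.0 (10% vs 5%) is displayed as 1.83 to 1.17 for prevalence between 1% and 20%. These figures rest on assumed rates and full persistence. The effect is near nil for criteria that are rare at MNT baseline, such as QTc of 500 msec or more, and larger for any criterion that is common there. Which criteria those are cannot be settled from the documents.

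Two stronger readings are not supported: that the plan conceals new abnormalities, since listings and shift tables recover part of the information; and that pre-existing cases necessarily enter the arms equally.

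The induction-ECG condition in SAP 7.5 serves no purpose with limits on the observed value. The documents do not say how many subjects it would affect, and an excluded case should still appear in the ECG PCI listing.

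**What to change.** In SAP 7.2 and 7.5, keep the present all-subject PCI count and add two rows by arm for each criterion.

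- **Row 1, new-onset PCI.** Numerator: subjects not PCI on that criterion at MNT baseline, with at least one post-MNT PCI value. Denominator: subjects not PCI on it at MNT baseline, with at least one post-MNT value. Subjects with a missing MNT baseline stay in.
- **Row 2, PCI at MNT baseline and again afterwards.** Numerator: subjects PCI on that criterion at MNT baseline, with at least one post-MNT PCI value. Denominator: subjects PCI on it at MNT baseline, with at least one post-MNT value. This keeps persistence on ontamalimab versus resolution on placebo visible.

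The two numerators add up to the all-subject count.

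In SAP 7.5, delete the requirement for an available induction baseline ECG from both the PCI numerator and denominator.

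The cost is SAP wording, one MNT-baseline flag per criterion in the analysis datasets, two extra rows, and denominators that differ by parameter. Trial conduct is unaffected.

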7.3 Pregnancy Test and Follicle-stimulating Hormone Test

Pregnancy tests are not required for females of nonchildbearing potential. All pregnancy tests data will be listed for the Safety Set.

7.4 Vital Signs

Descriptive statistics for vital signs (eg, systolic and diastolic blood pressure, pulse rate, body weight, respiratory rate, and temperature) and their changes from induction study (SHP647-301 or SHP647-302) baseline at each post-baseline visit and at the end of the study will be presented by treatment group as listed in Appendix 16.6.

For pulse rate, a post-MNT baseline value is considered as a PCI value if it meets both criteria for observed value and change from induction study (SHP647-301 or SHP647-302) baseline. For systolic/diastolic blood pressure, a post-MNT baseline value is considered as a PCI value if it meets criteria for observed value or change from induction study (SHP647-301 or SHP647-302) baseline. For weight and BMI, a post-MNT baseline value is considered as a PCI value if it meets criteria for change from induction study (SHP647-301 or SHP647-302) baseline. The PCI criteria are listed in Table 4. The number and percentage of subjects with PCI post-MNT baseline values will be tabulated by treatment group as listed in Appendix 16.6. The percentages will be calculated relative to the number of subjects with induction study (SHP647-301 or SHP647-302) baseline and at least 1 post-MNT baseline assessment. The numerator is the total number of subjects with at least 1 PCI post-MNT baseline vital sign value. A supportive listing of subjects with post-MNT baseline PCI values will be provided including the subject number, site, induction study (SHP647-301 or SHP647-302) baseline, MNT baseline, and post-MNT baseline values.

All vital signs data will be listed for the Safety Set.

7.5 Electrocardiogram (ECG)

Table 4: Criteria for Potentially Clinically Important Vital Signs

Vital Sign Parameter	Flag	Criteria ^a	
		Observed Value	Change from MNT Baseline
Systolic blood pressure (mmHg)	High	≥180	Increase of ≥20
	Low	≤90	Decrease of ≥20
Diastolic blood pressure (mmHg)	High	≥105	Increase of ≥15
	Low	≤50	Decrease of ≥15
Pulse rate (beats per minute)	High	≥120	Increase of ≥15
	Low	≤50	Decrease of ≥15
Weight (kg)	High	-	Increase of ≥7%
	Low	-	Decrease of ≥7%
BMI (kg/m ²)	High	-	Increase of ≥10%
	Low	<18	Decrease of ≥10%
Temp. (°C)		NA	NA

^a For pulse rate, a post-baseline value is considered as a PCI value if it meets both criteria for observed value and change from MNT baseline. For systolic/diastolic blood pressure, a post-baseline value is considered as a PCI value if it meets criteria for observed value or change from MNT baseline. For weight and BMI, a post-baseline value is considered as a PCI value if it meets criteria for change from MNT baseline.

A central ECG reader will be used. Descriptive statistics for ECG variables (eg, heart rate, PR interval, QRS interval, QT interval, QTc interval, QTcB, and QTcF) and their changes from induction study (SHP647-301 or SHP647-302) baseline at each assessment time point will be presented by treatment group as listed in Appendix 16.6.

Electrocardiogram interpretation will be summarized by visit. A shift table from induction study (SHP647-301 or SHP647-302) baseline to each visit for qualitative ECG results will be presented by treatment group as listed in Appendix 16.6.

Electrocardiogram variable values will be considered PCI if they meet or exceed the upper limit values listed in Table 5. The number and percentage of subjects with available induction study (SHP647-301 or SHP647-302) baseline values and post-MNT baseline PCI values will be tabulated by treatment group as listed in Appendix 16.6. The percentages will be calculated relative to the number of subjects with available induction study (SHP647-301 or SHP647-302) baseline values and at least 1 post-MNT baseline assessment. The numerator is the total number of subjects with at least 1 post-MNT baseline PCI value.

Listings of ECG data including the central reader's assessment and investigator's interpretation by individual subject will be produced. Separate listings will be produced for subjects with ECG results meeting the PCI criteria. Data from unscheduled visits will be listed, but not summarized.

Table 5: Criteria for Potentially Clinically Important ECG Values

ECG Parameter	Unit	Higher Limit
QRS Interval	msec	≥150
PR Interval	msec	≥250
QTc Interval	msec	≥500

ECG=electrocardiogram

